
Objective: The primary objective of this study is to determine the ability of a ^{13}C-urea breath test to detect urease producing pathogens in patients with pneumonia as confirmed on sputum culture results. Additional objectives of this study will include:
 
 • Determine optimal times for post-nebulization breath collection • Evaluate the safety and tolerability of the ^{13}C-urea breath test in patients with pneumonia 	

Methodology: This is a Phase 1, open-label evaluation of an inhaled ^{13}C-urea breath test in the identification of urease positive bacteria in patients diagnosed with pneumonia in the emergency department (ED). This study will enroll up to 75 adult male and female subjects at two US sites in two cohorts. Adult subjects will be screened for participation in two dosing cohorts to be enrolled sequentially. Cohort A will enroll 15 subjects presenting to the study sites with pneumonia symptomatology that is planned for outpatient treatment. Following enrollment and review of the safety of dosing in Cohort A, subjects receiving a diagnosis of pneumonia in the ED that are planned for admission will be screened for enrollment in Cohort B. Eligible subjects will provide informed consent, medical history, and samples for laboratory testing (including pregnancy testing for females of childbearing potential) during screening. Subjects will be evaluated for their CURB-65 Pneumonia Severity Score, and Community-Acquired Pneumonia Severity Index (PSI) where required data are available. Prior to breath test administration, Cohort B subjects will provide a oropharyngeal swab for bacterial identification via next generation sequencing (NGS) plus a sputum sample for bacterial culture and NGS; the sputum sample may be induced, or collected as part of initial ED workup if appropriate culture has been ordered. Subjects will undergo breath test with collection of baseline breath samples (up to 6), followed by complete nebulization of ^{13}C-urea solution. Immediately following the end of nebulization, breath collection bag samples will be collected at up to 6 time points with at least 1 minute intervals within 10 minutes post-nebulization. Exhaled breath bags will be centrally processed to determine the change in exhaled $^{13}\text{CO}_2$ levels. Vital signs, including resting blood pressure, resting pulse, respiratory rate, peripheral oxygen saturation, and temperature will be collected prior to, and following completion of, nebulization treatment. In the event of bronchospasm, during or following nebulization, albuterol rescue will be available for treatment at the discretion of the investigator. Once required tests are complete, the subject will be treated/followed according to standard institutional protocol/practice. The subjects' clinical course will be followed for at least 24 hours, where possible, to document the final diagnosis and outcome.
	

SYNOPSIS (PAGE 2 OF 4)

Name of Sponsor/Company: [name], PhD University of New Mexico	Protocol Number: 16-327
Name of Study Drug/Device: ^{13}C -Urea solution for nebulization	Protocol Title: A Phase 1, open-label, evaluation of a ^{13}C -urea breath test for the detection of urease-producing bacteria in patients with pneumonia in the emergency dept.
Name of Active Ingredient: ^{13}C -urea	Phase of Development: 1
Number of subjects to be enrolled: This study will enroll up to 75 adult male and female subjects in two dosing cohorts.	
Number of study sites: 2	Study country location: United States
Criteria for inclusion: Subjects must meet all of the following criteria to be considered eligible for the study:	
Cohort A Only:	

 1. be a man or woman age 18-70, inclusive 2. have suspected bacterial pneumonia on presentation to the study site based on clinical signs and symptoms 3. be expected to be treated on an outpatient basis in the opinion of the treating clinician at time of enrollment OR a definitive decision to admit has not been made, and the subject meets ALL of the following criteria; Pulse <125 beats per minute, Systolic blood pressure ≥ 100 mmHg, Respiratory rate ≤ 24 breaths per minute, Temperature $>35\text{C}$, and Temperature $<40\text{C}$. Subjects who are expected to be placed in an ED observation unit are eligible if they meet all of the defined vital sign criteria 	
Cohort B Only:	

 4. be a man or woman age 18-85, inclusive, 5. have a diagnosis of suspected bacterial pneumonia on presentation to the study site based on findings of a positive chest x-ray or advanced radiology and clinical signs and symptoms 6. be planned for admission to the hospital ward/floor in the opinion of the treating clinician at time of enrollment 7. be capable of providing a spontaneous or induced sputum for analysis 	
Both Cohorts A and B:	

 8. be capable of completing the breath test according to the clinical judgement of the investigator 9. be able to understand the study procedures, agree to participate in the study program, and voluntarily provide written informed consent 	
Criteria for exclusion: Subjects who meet any of the following criteria will be excluded from the study:	

 1. have a known allergy to urea or any excipient in the nebulized solution 2. be pregnant or have a positive urine pregnancy test 3. have evidence of active oral infection, such as abscess or dense exudate, that requires antibiotic therapy 4. have known diagnosis of cystic fibrosis or bronchiectasis 5. have a known or suspected acute asthma exacerbation on presentation 6. have received treatment with oral or intravenous (IV) antibiotics in the preceding 2 days prior to screening, unless antibiotic failure is suspected 	
OR	
Cohort A: have received treatment with oral or IV antibiotics greater than 6 hours prior to breath test	
Cohort B: have received treatment with oral or IV antibiotics greater than 4 hours prior to breath test	

 7. have an acute illness or other condition that, as determined by the investigator, would preclude participation in the study 	

SYNOPSIS (PAGE 3 OF 4)

Name of Sponsor/Company: [name], PhD University of New Mexico	Protocol Number: 16-327
Name of Study Drug/Device: ^{13}C -Urea solution for nebulization	Protocol Title: A Phase 1, open-label, evaluation of a ^{13}C -urea breath test for the detection of urease-producing bacteria in patients with pneumonia in the emergency department.
Name of Active Ingredient: ^{13}C -urea	Phase of Development: 1
Investigational product: ^{13}C -urea solution for nebulized administration	
Reference therapy: NA	
Duration of treatment: Enrolled subjects will receive a single nebulized dose of ^{13}C -urea with subsequent breath collection. Subjects will complete all study evaluations during a single ED visit.	
Criteria For Evaluation	

Efficacy: Efficacy endpoints will include the following:
 
 • Evaluate the exhaled $^{13}\text{CO}_2$ levels at each time point post-nebulization • Evaluate the relationship between the exhaled $^{13}\text{CO}_2$ levels at each time point and subject's causative pathogen based upon sputum culture or NGS • Evaluate the sensitivity and specificity of the ^{13}C-urea breath test for urease producing pathogens • Evaluate the positive and negative predictive value of the ^{13}C-urea breath test for urease producing pathogens • Correlation of the ^{13}C-urea breath test with CURB65 in subjects with sputum cultures positive for urease pathogens • Correlation of the ^{13}C-urea breath test with PSI in patients with sputum cultures positive for urease pathogens • Univariate association of all study variables with urease pathogen caused pneumonia • Multi-variate logistic regression model for urease pathogen caused pneumonia utilizing study variables that are significant in univariate analysis to compute odds ratio for each model variable and overall explanation of variance by model 	

Safety: Safety endpoints will include:
 
 • Incidence of adverse events (AEs) • Incidence of death, transfer to ICU, or intubation 	

SYNOPSIS (PAGE 4 OF 4)

Name of Sponsor/Company: [name], PhD University of New Mexico	Protocol Number: 16-327
Name of Study Drug/Device: ^{13}C -Urea solution for nebulization	Protocol Title: A Phase 1, open-label, evaluation of a ^{13}C -urea breath test for the detection of urease-producing bacteria in patients with pneumonia in the emergency department.
Name of Active Ingredient: ^{13}C -urea	Phase of Development: 1
Statistical methods:	
Sample size determination: The sample size for this study was selected based on prior exposures and existing safety data. Descriptive statistical analysis of results are planned as findings from this study will be used in order to appropriately determine the sample size requirements for future definitive evaluations of inhaled ^{13}C -urea in an adequately powered study of efficacy in this population.	
Study populations: Intent-to-Treat (ITT) Analysis Set: The ITT set will include all subjects who receive nebulized ^{13}C -urea. The ITT analysis set is also referenced as the Safety Analysis Set. Safety analysis will be performed using the ITT set. Modified Intent-to-Treat (mITT) Analysis Set: The mITT subjects include all ITT subjects who provide at least one post-dose breath sample. Efficacy analysis will be performed on the mITT analysis set.	
Efficacy analysis: Breath test exhaled $^{13}\text{CO}_2$ results at each time point will be presented for the overall population for determination of optimal breath sampling time. Relationship between the exhaled $^{13}\text{CO}_2$ at each time and subject's pneumonia diagnosis and pathogen (determined by sputum culture or NGS) will be examined. The time point where exhaled $^{13}\text{CO}_2$ can reliably predict the presence of urease positive pathogen in subjects with pneumonia diagnosis will be considered as the optimal time for ^{13}C -urea breath test sampling. The proportion of subjects with breath test positive/negative determination will be compared to sputum culture or NGS results when available. Correlation analyses will be performed where sufficient data are available.	
Safety analysis: The Medical Dictionary for Regulatory Activities (Version 18 or higher) will be used to classify all AEs with respect to system organ class and preferred term. AEs will be summarized for the safety analysis set.	

TABLE OF CONTENTS

SYNOPSIS (PAGE 1 OF 4)	3
TABLE OF CONTENTS.....	7
LIST OF ABBREVIATIONS.....	11
1. INTRODUCTION	12
2. STUDY OBJECTIVE.....	14
3. INVESTIGATIONAL PLAN.....	15
3.1. Overall Study Design.....	15
3.2. Rationale for Study Design and Control Groups.....	16
3.3. Clinical Study Sites.....	16
4. STUDY POPULATION.....	17
4.1. Inclusion Criteria	17
4.2. Exclusion Criteria	17
4.3. Discontinuation of Subjects.....	18
4.3.1. Procedures for Withdrawal	18
4.3.2. Replacement of Subjects.....	18
4.4. Lifestyle Guidelines.....	18
4.4.1. Confinement	18
4.4.2. Diet	18
5. TREATMENTS.....	19
5.1. Administration of Study Medication	19
5.2. Identity of Study Medication	19
5.3. Method of Assigning Subjects to Treatment Groups	19
5.4. Selection of Doses	19
5.5. Selection of Timing of Dose.....	19
5.6. Blinding and Unblinding of Study Medications.....	19
5.7. Treatment Compliance.....	19
5.8. Drug Accountability	20
5.9. Packaging, Labeling, and Storage	20

1. INTRODUCTION

Rapid identification of respiratory pathogens remains a global concern affecting initiation of therapy, and pharmacotherapy selection. The lack of rapid point of care tests that can provide clinicians with some indication of which pathogen(s) is causing disease may lead to selection of inappropriate therapy, in particular to overuse of broad spectrum antibiotics.

Urease producing organisms represent a virulent set of pathogens which may be present in respiratory infections including *Pseudomonas aeruginosa*, *Staphylococcus aureus*, and *Klebsiella pneumoniae*. Identification of the presence or absence of urease activity may allow clinicians to narrow the spectrum of suspected infections, confirming the need for antimicrobial therapy and influencing therapy selection.

The breath test is based upon a modification of existing breath testing technology that detects and monitors a biomarker associated with peptic ulcers. The mechanism of action for detecting urease-containing bacteria in the lungs is the same as for detecting another urease-containing bacterium, *Helicobacter pylori*, in the stomachs of patients with peptic ulcers.

For the intended indication, inhaled ^{13}C -urea will be catalytically hydrolyzed into ^{13}C -carbon dioxide ($^{13}\text{CO}_2$) if urease is present in the bacterial pathogens causing the pneumonia (I).

CO_2 contains predominantly ^{12}C but a small amount of ^{13}C is present. Since the urea is produced with ^{13}C -urea all CO_2 generated by hydrolysis with urease will be $^{13}\text{CO}_2$. By measuring the ratio of $^{13}\text{CO}_2/^{12}\text{CO}_2$ in exhaled breath samples before and after inhalation of ^{13}C -urea, the presence of urease-containing bacteria can be detected. In the absence of urease-containing bacteria in the lungs, the isotopic ratio of $^{13}\text{C}/^{12}\text{C}$ in the baseline and test breath samples will be approximately the same. If urease-containing bacteria are present within the lungs, the concentration of exhaled $^{13}\text{CO}_2$ will be increased measurably in the test breath sample relative to baseline. It is anticipated that urease-producing bacteria can be detected within 5 minutes of initiating the breath test.

The University of New Mexico conducted a proof of concept study of the ^{13}C -urea Breath Test in 3 normal volunteers and 3 Cystic Fibrosis (CF) patients with known pseudomonas colonization. Two doses of isotonic ^{13}C -urea (20 mg and 50 mg) were used. All doses were tolerated well with no significant AEs. The exhaled $^{13}\text{CO}_2$ was higher in the CF subjects with both doses but separation was better with the 50 mg dose. In this study the first breath samples were taken at 5 minutes after ^{13}C -urea nebulization and results rapidly declined in the next samples. These results suggest that breath sampling should be started sooner after the completion of nebulization of the ^{13}C -urea

Mycobacteria tuberculosis contains urease and ^{13}C -urea breath test was shown to detect TB in a rabbit model. Subsequently a study has been initiated in patients with suspected TB infection in South Africa. This study has evaluated the administration of a 50 mg nebulized dose of ^{13}C -urea with subsequent breath collection and analysis for exhaled $^{13}\text{CO}_2$ concentrations. This study has administered doses of ^{13}C -urea to over 100 subjects for TB screening. Doses were well tolerated

PROTOCOL 16-327

with a low incidence of mild AEs and no nebulization treatments requiring premature discontinuation.

The current study is proposed to expand the experience of ^{13}C -urea testing in patients with a diagnosis of pneumonia in the ED. This study will evaluate the tolerability of dosing in this population, as well as the correlation of testing results with bacterial culture observations.

2. STUDY OBJECTIVE

The primary objective of this study is to determine the ability of the ¹³C-urea breath test to detect urease producing pathogens in patients with pneumonia as confirmed on sputum culture results.

Additional objectives of this study will include:

- Determine optimal times for post-nebulization breath collection
- Evaluate the safety and tolerability of the ¹³C-urea breath test in patients with pneumonia

3. INVESTIGATIONAL PLAN

3.1. Overall Study Design

This is a Phase 1, open-label evaluation of an inhaled ¹³C-urea breath test in the identification of urease positive bacteria in patients diagnosed with pneumonia in the emergency department (ED). This study will enroll up to 75 adult male and female subjects at two US sites in two cohorts.

Adult subjects will be screened for participation in two dosing cohorts to be enrolled sequentially. Cohort A will enroll 15 subjects presenting to the study sites with pneumonia symptomatology that is planned for outpatient treatment. Following enrollment and review of the safety of dosing in Cohort A, subjects receiving a diagnosis of pneumonia in the ED that are planned for admission will be screened for enrollment in Cohort B. Eligible subjects will provide informed consent, medical history, and samples for laboratory testing (including pregnancy testing for females of childbearing potential) during screening. Subjects will be evaluated for their CURB-65 Pneumonia Severity Score, and Community-Acquired Pneumonia Severity Index (PSI) where required data are available.

Prior to breath test administration, Cohort B subjects will provide a sputum sample for bacterial culture; sample may be induced, or collected as part of initial ED workup if appropriate culture has been ordered. Subjects will undergo breath test with collection of baseline breath samples (up to 6), followed by complete nebulization of ¹³C-urea solution. Immediately following the end of nebulization, breath collection bag samples will be collected at up to 6 time points with at least 1 minute intervals within 10 minutes post-nebulization. Exhaled breath bags will be centrally processed to determine the change in exhaled ¹³CO₂ levels. Vital signs, including resting blood pressure, resting pulse, respiratory rate, peripheral oxygen saturation, and temperature will be collected prior to, and following completion of, nebulization treatment. In the event of bronchospasm, during or following nebulization, albuterol rescue will be available for treatment at the discretion of the investigator.

After administration of nebulized ¹³C-urea solution, subjects will be monitored at the study site for any adverse events. Adverse events directly related to nebulizer administration would be expected to present within minutes of nebulization. Evidence shows that, generally, symptoms of anaphylaxis appear between 1-15 minutes after exposure to an agent. Symptoms of anaphylaxis may present as lightheadedness, dizziness, difficulty breathing, wheezing, hives, swelling under the skin, rashes, and/or nausea. The study team will monitor subjects for 20 minutes after nebulization for any adverse events. All subjects will receive standard care in the hospital setting prior to and after completion of study procedures. Subjects will sign and be given a copy of the consent form which has contact information and instructions that they should return to the emergency department if they suspect they are suffering from any symptoms related to the nebulization. The instructions in the consent form also specify that, if returning to the emergency department at the corresponding study site with symptoms they believe are due to the study, they should bring the consent form with them to the ED and ask that the study site Principal Investigator be immediately called and notified on their return. In Cohort A, all safety observations prior to discharge, and in Cohort B the clinical course over the hospital admission,

will be reviewed and submitted to the safety monitoring committee as described below in Sections 7 and 8.

Once required tests are complete, the subject will be treated/followed according to standard institutional protocol/practice. The subjects' clinical course will be followed for at least 24 hours, where possible, to document the final diagnosis and outcome.

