6.3.3. Follow-Up Contact

After 48 hours post breath test administration, all subjects will receive a follow-up safety contact. The safety contact should be completed between 48 and 96 hours post breath test administration. For subjects who have been discharged, follow-up contact will be performed via telephone contact (up to 3 attempts) by a study investigator or designee. For subjects who remain inpatient at the hospital, the follow-up will be performed in person. Safety follow-up will include a chart review as well as discussion with the subject regarding their treatment course and current status.

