6.4.3. Follow-Up

All subjects will undergo follow-up 48 hours following breath test administration to include:

- Follow-up Safety Contact ([Section 6.3.3](#))
- Monitoring of AEs ([Section 7](#))

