7.1. Definition of an Adverse Event

An AE is defined as any untoward medical occurrence associated with the use of a drug in humans, whether or not considered drug related.

An AE may be any unfavorable and unintended sign (including an abnormal laboratory finding), symptom, or disease temporally associated with the use of a study medication, whether or not considered causally associated with the use of the study medication. Any abnormal laboratory value deemed clinically significant by the investigator, regardless of causal relationship, must be reported as an AE.

Examples of an AE include the following:

- significant or unexpected worsening or exacerbation of the condition or indication under study
- exacerbation of a chronic or intermittent preexisting condition, including either an increase in frequency or intensity of the condition (e.g., abnormal physical examination finding)
- signs, symptoms, or clinical sequelae of a suspected interaction
- signs, symptoms, or clinical sequelae of a suspected overdose of the study medication or a concurrent medication (overdose per se should not be reported as an AE or SAE, unless nonserious or serious sequelae occur)

The following examples are not considered AEs:

- medical or surgical procedure (e.g., endoscopy, appendectomy), although the condition that leads to the procedure is an AE
- anticipated day-to-day fluctuations of preexisting disease(s) or condition(s) (including laboratory values) present or detected at the start of the study that do not worsen
- the disease or disorder being studied, or expected progression, signs, or symptoms of the disease or disorder being studied, unless they become more severe or occur with a greater frequency than expected for the subject's condition

All AEs, whether volunteered, elicited, or noted on physical examination, and regardless of causality or seriousness, will be assessed and recorded on the CRF beginning after administration of study medication through approximately 2 hours after administration. SAEs (see [Sections 7.2](#) and [7.3](#)) will be assessed and recorded after administration of study medication through the last study follow-up (as described in [Section 6.4.3](#)).

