4.9.1 Adverse Event/Serious Adverse Event Reporting

This study is a non-interventional study. The only study related procedure the patient will experience is the urea breath test. Adverse events will be collected up until 48 hours post administration of the study drug and any noted adverse events from this time period will be followed till resolution.

A patient may experience an adverse event related to the urea breath test, which is defined as but not limited to coughing, dizziness, feeling faint or fainting. If a patient were to experience an adverse event, this must be recorded in the CRF. If the adverse event is deemed to be serious, the event must be reported by the site investigator or his/her designate to the safety monitor ([name] of UNMHSC) and the study PI ([name] of UNMHSC-EM) as soon as possible. In addition, notification shall be given in writing to the FDA and the site's IRB per the IRB's internal procedures.

Serious is defined as either:

- ◆ Death,
- ◆ Life-Threatening,
- ◆ Unanticipated Hospitalization (initial or prolonged),
- ◆ Disability,
- ◆ Congenital Anomaly, or
- ◆ Requiring Intervention to Prevent Permanent Impairment or Damage.

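### Non-serious AEs are recorded to about 2 hours in 7.1 but collected to 48 hours in Appendix E, and the review that opens Cohort B does not require the 48-96 hour contacts

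*Combined protocol and SAP*

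**What the plan says.** **Recording window.** Section 7.1 says that all AEs, serious or not, "will be assessed and recorded on the CRF beginning after administration of study medication through approximately 2 hours after administration". Only SAEs run on to the last study follow-up. The monitoring plan in Appendix E 4.9.1 says "Adverse events will be collected up until 48 hours post administration of the study drug", does not limit this to serious events, and has them followed to resolution. Section 6.4.3 opens "All subjects will undergo follow-up 48 hours following breath test administration to include" and then lists the safety contact and AE monitoring, with a reference back to Section 7.

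**Bedside observation.** Section 3.1 states: "The study team will monitor subjects for 20 minutes after nebulization for any adverse events". It gives reasons: events related to the nebulizer are expected within minutes, and anaphylaxis generally appears 1 to 15 minutes after exposure.

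**Later contact.** Section 6.3.3 sets a safety contact at 48 to 96 hours, by telephone (up to three attempts) for discharged subjects. On content it says: "Safety follow-up will include a chart review as well as discussion with the subject regarding their treatment course and current status". Two other routes exist for subjects who have left. The consent form tells them that "they should return to the emergency department if they suspect they are suffering from any symptoms related to the nebulization", and under 3.1 their "clinical course will be followed for at least 24 hours, where possible, to document the final diagnosis and outcome".

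**Safety review.** Section 3.1 describes what goes to the safety committee: "In Cohort A, all safety observations prior to discharge, and in Cohort B the clinical course over the hospital admission", as set out in Sections 7 and 8. Section 6.6 requires an overall safety review of Cohort A, following enrollment of its 15 subjects, before Cohort B opens. Section 8.1 has the committee review each subject's safety experience and cumulative AEs. Section 8.4 schedules group reviews, four of which cover subjects 1 to 15.

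**Analysis.** The incidence of all AEs is a safety endpoint (9.2.2). Section 9.6.2 tabulates AEs by cohort and overall and names no onset window.

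**The concern.** Safety and tolerability is a stated objective, and the AE table is how the study reports it. If two parts of the same document set different recording periods, the table has no single definition. Site staff working to 7.1 could leave out a non-serious event that a monitor working to Appendix E, with 100% source verification, would expect to find. The by-cohort and overall counts would then depend partly on which section was followed. Unrecorded non-serious events may not be recoverable later.

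The second issue is the step from Cohort A, planned for outpatient care, to Cohort B, planned for admission. That step rests on the Cohort A safety review. Nothing in 3.1, 6.6, Section 8 or the review form in Appendix C.1 says that the review must wait for the post-discharge contacts. Appendix E 4.2 does make the second Cohort A monitoring visit wait for the follow-up call, so the plan applies the idea to a site visit but not to the safety decision.

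**Working it through.** The plan gives no figure to reproduce here. The check compares the texts, with one illustration and one timeline.

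**1. The two recording windows.** Section 7.1 gives about 2 hours and Appendix E 4.9.1 gives 48 hours. The gap is 48 - 2 = 46 hours, and the shorter window is 2/48 = 4.2% of the longer.

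**2. A test case.** Take a Cohort A outpatient with a non-serious AE starting 6 hours after dosing.
- 7.1: outside the window, not recorded.
- Appendix E 4.9.1: inside the window, recorded and followed to resolution.
- 6.4.3: AE monitoring takes place at 48 hours, but under Section 7, whose window for non-serious events has closed.
- 7.6: requires review at later contacts of AEs already documented; this one is not documented.
- 9.2.2 and 9.6.2: name no window, so they do not settle it.

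The same event is in or out of the endpoint according to the section followed.

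**3. What the choice could do to Cohort A (illustration; p and f are assumptions, not in the documents).** Let p be the true chance that a subject has a non-serious AE with onset within 48 hours, and f the share of those with onset within 2 hours. The chance that at least one of 15 subjects has a recordable AE is 1 - (1 - p)^15 under 48 hours and 1 - (1 - p × f)^15 under 2 hours.

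| p | 48-hour window | 2-hour window, f = 50% | 2-hour window, onset uniform over 48 h (f = 4.2%) |
|---|---|---|---|
| 5% | 54% | 32% | 3% |
| 10% | 79% | 54% | 6% |
| 20% | 96% | 79% | 12% |

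For example, at p = 10% and f = 50%: 1 - 0.90^15 = 0.794 and 1 - 0.95^15 = 0.537. If every AE starts within 2 hours (f = 100%), the two windows agree. Section 3.1 expects related events within minutes. The endpoint counts AEs regardless of causality, so f need not be 100%, but the documents give no onset data to place it.

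**4. The gate.** A subject dosed at time d has the contact between d + 48 h and d + 96 h. At a review held at time T:
- dosed less than 48 hours before T: the contact cannot yet have happened;
- dosed 48 to 96 hours before T: it may not have happened;
- dosed more than 96 hours before T: the contact window has closed.

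If contact data are used as they arrive, only Cohort A subjects dosed in the 96 hours before the review can lack them. How many of the 15 that is depends on the enrollment rate and the review date, which the documents do not give. A review held right after the last dose would lack at least that subject's contact; one held more than 96 hours after it need lack none. The plan does not choose between these.

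**The case against.** **7.1 already governs.** The introduction to Appendix E says the monitoring plan exists to verify that the study follows the protocol, which suggests that the body controls. AE monitoring in 6.4.3 refers back to Section 7 and can be read as SAE detection plus follow-up of AEs already documented. This is a fair reading, but it is nowhere stated. Appendix E is part of the protocol, 10.2 points to it, and its 48-hour sentence is not limited to serious or previously recorded events.

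**Late events are largely captured.** 6.3.3 describes a safety contact with chart review and discussion, and its wording is not an exhaustive list. This stands, and it is why the change is small. Still, the contact does not direct staff to ask about AEs since dosing.

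**The review is broad.** An overall review under 6.6 and cumulative AEs under 8.1 do not exclude contact data, and 3.1 does not say that only pre-discharge data may be sent. This stands against the stronger reading below, but it does not answer the timing question.

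**The stakes are modest.** This is a single-dose, descriptive study. The plan reports more than 100 earlier exposures without SAEs and, in the tuberculosis study, a low incidence of mild AEs. This stands.

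A reader might also infer more than the text supports:
- *That the 20 minutes in 3.1 is a third conflicting window.* Bedside observation and CRF recording need not have the same length, and 3.1 justifies the 20 minutes.
- *That subjects leave at minute 20 and their later AEs are lost.* No section says so. 7.1 sets an assessment duty to about 2 hours, and Cohort A may include observation-unit patients.
- *That contact data are barred from the gate for all 15 subjects.* This reads 3.1 as an exclusion and sets aside 6.6 and 8.1.

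**Conclusion.** Two points hold. First, the recording window for non-serious AEs is about 2 hours in 7.1 and 48 hours in Appendix E 4.9.1, with 6.4.3 scheduling AE monitoring at 48 hours. The all-AE incidence endpoint therefore depends on the rule followed. Second, the text allows the Cohort A review to take place, and Cohort B to open, before the 48-96 hour contacts for the most recently dosed Cohort A subjects are available.

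The size is unknown and may be nil, since the documents give no AE rate or onset times. The illustration shows only that the window can matter if a fair share of AEs start after 2 hours. It does not show that they do.

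A reader might infer that serious events could slip past the gate. For known SAEs the documents do not support this: they are recorded through the last follow-up (7.1), reported within 24 hours (7.7), and halt enrollment pending review (6.6). Only an SAE first learned of at the contact could be missing. This is a minor-to-moderate point, worth acting on because the correction is cheap.

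**What to change.** 1. Change 7.1 to record all AEs through 48 hours, matching Appendix E 4.9.1 and 6.4.3. In 6.3.3, have the existing 48-96 hour contact ask every subject about AEs since dosing. The contact falls at or after the end of the 48-hour window, so no new contact is needed. The 20-minute observation in 3.1 can stay as it is.
2. State in 3.1 and 6.6 that the Cohort A review takes place only after the contact, or three failed attempts, for all 15 subjects, and that it includes those data before Cohort B opens.

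The cost is a few sentences and one question at a planned contact, with no extra visits or subjects. There are two downsides. Cohort B may wait up to about 96 hours after the last Cohort A dose. Some recalled or disease-related non-serious AEs will enter the tables, although 7.1 already excludes expected progression of the pneumonia.
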